2.2.8 Hepatitis panel

- Hepatitis B surface antigen (HBsAg)
- Hepatitis C virus antibody (anti-HCV) (or Hep C RNA-PCR if antibody positive)

Test results must be negative for trial entry.

2.2.9 HIV

Human immunodeficiency virus antibody titer test results must be negative for trial entry.

2.2.10 Autoimmune panel

- Antithyroglobulin antibody
- Antinuclear antibody (ANA) test, if positive test for Extractable nuclear antigen (ENA), if ENA positive, then the following tests will be performed (If negative, then a sample of serum will be stored for subsequent testing in the event that the ANA becomes positive):
 - Anti-phospholipid antibody
 - Anti-neutrophil cytoplasm antibody
 - CH50
 - Anti-DNA antibody
 - Anti-SSA antibody
 - Anti-SSB antibody
 - Rheumatoid factor (RF)

2.2.11 Thyroid function test

Thyroid stimulating hormone (TSH) – if abnormal, run full Thyroid function test (TFT panel, including Free T3 and Total T4).

2.2.12 Hematology

- Hemoglobin
- Hematocrit
- Complete blood cell count with differential and platelet count (direct) and sedimentation rate

2.2.13 Biochemistry

In this study, patients will receive 3 mg/kg MDX-010 antibody intravenously every three weeks. Our experience with MDX-010 in patients with melanoma or renal cell cancer has shown a correlation between severe autoimmunity and tumor response. It has also shown a higher rate of both autoimmune toxicity and tumor response when MDX-010 is administered at repeated doses of 3 mg/kg. Two separate groups of 21-41 patients will be treated with intravenous infusion of MDX-010 at 3mg/kg for all doses. One of the groups will have locally advanced disease, while the other group will have distant metastases. The two groups will be evaluated separately using the same single arm, two-stage phase II design described in Section 5.5.

Four doses will be designated as a course of therapy and evaluations will be conducted at the end of each course, 3 weeks after the 4th infusion. An informal interim evaluation may be performed 3 weeks after the 2nd infusion to rule out rapid disease progression, but the formal evaluation with tumor measurements will be performed approximately 3 weeks after the 4th dose. CT scanning may be performed at any time during protocol implementation in the event that there is clinical evidence of disease progression

Treatment will be limited to 2 courses of therapy. Patients that respond and subsequently relapse will be treated with additional courses of therapy. Patients may come off study at any time if rapid disease progression occurs.

Patients in the locally advanced disease cohort may experience sufficient tumor response that their disease is rendered resectable. If this occurs, these patients will be treated with standard pancreatic resection rendering them NED (no evidence of disease).

3.2 Drug Administration:

MDX-010: All MDX-010 doses will be administered as an intravenous infusion controlled by an infusion pump. For administration, MDX-010 is to be injected into the IV bag and diluted in 0.9% Normal Saline, USP, to a concentration between 0.2 mg/ml and 1 mg/ml as specified in Section 8.1, and should be administered over 90 minutes through an add-on filter set with 1.2 µm air-eliminating filter [REDACTED]

Do not administer as an i.v. push or bolus. If \geq Grade 3 bronchospasm or other hypersensitivity reaction occurs, the infusion should be discontinued and no additional MDX-010 should be administered.

Surgical guidelines

Patients in the locally advanced disease cohort may experience sufficient tumor response that their disease is rendered resectable. If this occurs, these patients will be treated with standard pancreatic resection rendering them NED (no evidence of disease).

Resections will generally consist of proximal pancreatectomy (Whipple's pancreaticoduodenectomy) or distal pancreatectomy. Rarely, unusual resections of the pancreas (pylorus preserving proximal pancreatectomy, total pancreatectomy, Appleby's procedure, middle segment pancreatectomy, dorsal pancreatectomy, etc.) will be completed at the discretion of the operating clinician. Proximal pancreatectomies will follow the procedure outlined by [REDACTED] with variation and vascular reconstruction as indicated by anatomical or tumor characteristics. Distal and other types of resection will follow standard procedures.

Postoperatively, patients will be monitored in the ICU and will be routinely intubated for the initial 12 hours. Patients will receive nasogastric decompression, fluid resuscitation, prophylactic antibiotics, and pancreatic enzyme replacement during the postoperative period. Characteristically, patients will have gastrostomy and feeding tubes placed without intra-abdominal drains. These are expected postoperative events and will not be considered toxicities.

3.3 Treatment Modifications:

3.3.1 MDX-010

There will be no intra-patient dose modifications of MDX-010. Patients will discontinue treatment with MDX-010 if they experience an adverse event felt to be possibly or probably related to MDX-010 antibody that meets the following criteria:

- A patient who requires systemic steroid therapy for any reason will not receive further treatment with MDX-010 but will be followed until off study criteria are met.
- Any infusion related reaction of \geq grade 3. Infusion related reactions are defined as acute reactions that develop and resolve within 48 hours of the start of an infusion. This includes reactions that are responsive to therapy within that time frame except for Grade 3 fever that resolves within 48 hours. Exclusions to discontinuing therapy will be made in the presence of an objective response when the toxicity resolves prior to the next infusion.
- Any autoimmune toxicity of $>$ grade 2 that has the potential to be life threatening with continued antibody administration and is not associated with a potential therapeutic response, except rash, vitiligo or asymptomatic autoantibody detection. An autoimmune reaction is defined as an inflammatory process that compromises the function of any organ and is not attributable to another etiology.
- Any autoimmune toxicity (any grade) that does not resolve by the time that additional dosing with MDX-010 is considered. Patients may delay subsequent doses in a course by up to a maximum of 3 weeks while awaiting resolution of an autoimmune toxicity.
- Uveitis or episcleritis that is symptomatic (causing eye pain, photosensitivity, or blurred vision)
- Exclusions to these criteria include inflammation of $<$ grade 4 that is attributable to a local anti-tumor reaction that could potentially be a therapeutic response. This

includes inflammatory reactions at the site of tumor resection or in draining lymph nodes, or in sites suspicious for metastasis.

If any two patients of the trial develop a \geq Grade III non-skin-related toxicity or grade IV skin-related toxicity attributable to the investigational agent, except for those noted above, that cannot be alleviated or controlled by appropriate care (see Sections 4.0 through 4.5) and/or steroid therapy within 14 days of the initiation of the supportive care and/or steroid therapy, accrual to this study will stop until the principal investigator, in consultation with the sponsors and NCI IRB, review the events to determine the need to revise the protocol and informed consent.

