4.1 Acute hypersensitivity

Acute hypersensitivity reactions to MDX-010 antibody should be managed as outlined below.

- For mild symptoms: (Localized cutaneous reactions such as mild pruritis, flushing, or rash.) Decrease the rate of infusion until recovery from symptoms, remain at bedside and monitor patient; complete MDX-010 antibody infusion at the initial planned rate. Diphenhydramine 50 mg, may be administered at the discretion of the treating physician.
- For moderate symptoms: (Any symptom not listed above (mild symptoms) or below (severe symptoms) such as generalized pruritis, flushing, rash, dyspnea, or hypotension with systolic BP >80 mmHg.) Interrupt MDX-010 antibody infusion, administer diphenhydramine 50 mg i.v., remain at bedside and monitor patient until resolution of symptoms. Corticosteroids may abrogate any immune response, but may be administered at the discretion of the treating physician. If systemic steroid therapy was not needed, then at the discretion of the treating physician, MDX-010 infusion may be resumed after recovery of symptoms. At the discretion of the treating physician, MDX-010 antibody infusion may be resumed at one half the initial infusion rate, then increased incrementally to the initial infusion rate. If symptoms develop after resumption of the infusion, the infusion should be discontinued and no additional MDX-010 should be administered. At the discretion of the treating physician, additional oral or i.v. antihistamine may be administered.
- For severe symptoms: (Any reaction such as life threatening bronchospasm, systolic blood pressure <80 mm Hg, or angioedema.) Immediately discontinue infusion of MDX-010 and initiate appropriate therapy (potentially to include epinephrine 1 mg i.v. or subcutaneously and/or diphenhydramine 50 mg i.v. or solumedrol 100 mg i.v.) as needed. Monitor patient until resolution of symptoms. No further MDX-010 will be administered.

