4.3 Treatment of \geq Grade III Autoimmune Adverse Events

For **skin-related** \geq Grade III autoimmune toxicity, including severe generalized pruritis or rash, symptomatic treatment will be given. The types of therapy may include local skin care, antihistamines, or corticosteroids (which can be local/topical or systemic) as clinically indicated. At the discretion of the principal investigator, patients experiencing a skin-related autoimmune toxicity \geq Grade III who have not required systemic steroids may resume MDX-010 once the skin symptoms improve (see Section 3.3.1). Patients who require systemic steroid therapy will not receive further treatments with MDX-010.

Treatment for **non-skin-related** autoimmune adverse events \geq Grade III will be prescribed as clinically indicated depending on the severity of the symptoms and/or physical manifestations. Treatment may include oral, locally-delivered (e.g., per rectum) or i.v. steroids and/or other supportive care. No further doses of MDX-010 will be given once a patient develops a \geq Grade III non-skin-related autoimmune adverse event attributable to the investigational agents or if the patient requires systemic steroid therapy.

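### Protocol 3.3.1 keeps an objective responder on MDX-010 after a resolved grade 3+ infusion reaction, where 3.2, 4.1 or 4.4 stops the drug permanently; no section shown says which prevails

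*Protocol*

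**What the plan says.** Protocol 3.3.1 (under Treatment Modifications) lists the adverse events that end MDX-010 dosing. One is an infusion reaction of grade 3 or higher, meaning an acute reaction that starts and clears within 48 hours of the start of the infusion. The same bullet spares grade 3 fever that clears in that window, and adds: "Exclusions to discontinuing therapy will be made in the presence of an objective response when the toxicity resolves prior to the next infusion".

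Other sections set stops without a responder exception:

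- **3.2 Drug Administration**, at or above the stated grade: "Grade 3 bronchospasm or other hypersensitivity reaction occurs, the infusion should be discontinued and no additional MDX-010 should be administered".
- **4.1 Acute hypersensitivity**, severe tier, described as "Any reaction such as life threatening bronchospasm, systolic blood pressure <80 mm Hg, or angioedema": "No further MDX-010 will be administered".
- **4.4** ends dosing after any attributable grade III or higher non-skin event not thought to be autoimmune.
- **4.3** ends dosing after any event at or above "Grade III non-skin-related autoimmune adverse event attributable to the investigational agents or if the patient requires systemic steroid therapy".

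For autoimmune toxicity above grade 2, 3.3.1 is narrower than 4.3. It requires a stop only when the event "has the potential to be life threatening with continued antibody administration and is not associated with a potential therapeutic response". A separate bullet stops dosing for autoimmune toxicity of any grade that has not resolved when the next dose is due, with a delay of at most 3 weeks. 3.3.1 also exempts inflammation below grade 4 put down to a local anti-tumor reaction.

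**The concern.** These rules decide whether a patient is re-exposed to the antibody after a serious reaction. If 3.3.1 and another section give opposite instructions for the same patient, two investigators can each follow the protocol and act differently, and a monitor cannot say which of them deviated. Following 3.3.1 means redosing after a reaction that the protocol elsewhere treats as a permanent stop.

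There is a cost on the other side too. The protocol reports a correlation between severe autoimmunity and tumor response, so a rule that always stops may take the drug from patients who are benefiting. Either policy can be defended, but the protocol should state which one it adopts.

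**Working it through.** No formula applies to the conflict itself, so the rules are set side by side. In the first two rows the patient has an objective response and the reaction resolves before the next infusion. All rows but the last assume an attributable event and no systemic steroids.

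| Event | 3.3.1 | Elsewhere | Can both be followed? |
|---|---|---|---|
| Grade 3+ bronchospasm or other hypersensitivity infusion reaction, responder | Exclusion to stopping is made | 3.2 stops; 4.1 stops if severe; 4.4 stops if non-skin and not autoimmune | No |
| Other grade 3+ infusion reaction, non-skin and not autoimmune, responder | Exclusion to stopping is made | 4.4 stops | No |
| Grade 3 fever clearing within 48 hours | No stop required | 4.4 stops | Yes, by stopping |
| Grade 3 non-skin local anti-tumor inflammation | Exempt | 4.4 stops (4.3 if judged autoimmune) | Yes, by stopping |
| Grade 3+ non-skin autoimmune event, not potentially life threatening or response-linked, resolved before the next dose | No stop required | 4.3 stops | Yes, by stopping |
| Any event needing systemic steroids | Stop | Stop | Yes |

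The first two rows differ from the rest because 3.3.1 words the responder exclusion as something that is done, not something that may be done. In the next three rows 3.3.1 merely does not demand a stop. For local inflammation, 4.4 is the more natural home, because 3.3.1 defines an autoimmune reaction as one with no other cause.

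**Is there a ranking rule?** None appears in the supplied text. 4.3 refers back to 3.3.1 for skin events only. The exception clause in the paragraph after the 3.3.1 criteria concerns the halt to accrual, not dosing of one patient. Sections 3.5 and 8.0 are in the contents list but are not shown, so the finding is limited to what can be read.

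**Does 4.1 settle the hypersensitivity boundary?** No. It sorts by symptom, while 3.2 and 3.3.1 sort by grade. Its moderate tier is residual ("Any symptom not listed above (mild symptoms) or below (severe symptoms"), and there, at the physician's discretion and without systemic steroids, "MDX-010 infusion may be resumed after recovery of symptoms". A grade 3 bronchospasm that is not life threatening is a permanent stop under 3.2 but could be handled as moderate under 4.1. The severe list is open-ended, so it could also be classed as severe.

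**When can the responder exclusion apply?**

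- Two courses of 4 give 2 × 4 = 8 doses, so 8 − 1 = 7 decisions to redose. Course 1 doses fall on days 0, 21, 42 and 63, and formal evaluation on day 63 + 21 = 84.
- If an unconfirmed response at that evaluation is enough, the exclusion can reach doses 5 to 8: 4 of 7 decisions.
- If the response must be confirmed at least 4 weeks later (Protocol 5.3.1.4), the earliest day is 84 + 28 = 112. With dose 5 on day 105 (infusion row of the Protocol schedule), later doses fall on days 126, 147 and 168: doses 6 to 8, or 3 of 7. With dose 5 on day 84 (SAP Table 1), doses fall on days 84, 105, 126 and 147: doses 7 and 8, or 2 of 7.
- A response seen earlier, on the informal evaluation after dose 2 or an unscheduled CT, would widen this. Retreatment after relapse could add up to 2 × 4 = 8 doses (SAP 2.2.1), but 3.3.1 does not say whether a relapsed patient still counts as having an objective response.

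**The case against.** The best defense is that 3.2 is the specific rule for grade 3+ hypersensitivity and 3.3.1 the general one, and that stops in several sections normally add up. On that view an investigator simply stops. Because 3.2 is graded, the tiers in 4.1 need not set the boundary; resumption in the moderate tier requires recovery and becomes a permanent stop if symptoms return. Other safeguards help: systemic steroids end treatment, the IRB reviews events monthly, and a new course requires toxicities of grade 1 or less after the first.

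Much of this stands. Stopping is the cautious reading, and the safeguards limit harm. But the specific-over-general reading is the reader's own; the protocol does not state it. It also does not fit 4.4, which is broader than the infusion-reaction bullet in 3.3.1, so there the more specific rule is the one that continues the drug. None of the safeguards says which section governs.

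A reader might infer that every exemption in 3.3.1 contradicts Section 4. The text does not support that: for fever, local inflammation and resolved autoimmune events, stopping complies with every section. Nor does 3.3.1 let autoimmune toxicity run on, since an unresolved event ends dosing there too.

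**Conclusion.** The contradiction is real and should be corrected. It covers objective responders with a grade 3+ infusion reaction that resolves before the next dose without systemic steroids. It is not confined to hypersensitivity, because 4.4 opposes the exclusion for other attributable non-skin, non-autoimmune reactions. The three further exemptions are a secondary point of clarity: as written they have no effect wherever 4.3 or 4.4 applies, or they invite a clinician relying on 3.3.1 to redose.

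The practical size in this trial was small. SAP 5.10 reports no clinical response in the first stage, which leaves the responder exclusion little or no scope. Had there been responders, it would mainly have mattered for 2 to 4 of the 7 redosing decisions, depending on confirmation and the day of dose 5. The other exemptions need no formal response evaluation and could arise at any of the 7. A reader might infer that patients were wrongly redosed; the documents give no event rates or dosing records, so nothing supports that. No sample size, error rate or analysis changes.

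This rests on the protocol text as supplied. The SAP describes features this text lacks, such as HAHA sampling, so a later version may have changed these rules.

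**What to change.** 1. In 3.3.1, limit the responder exclusion so that it never applies to grade 3+ bronchospasm or other hypersensitivity.
2. In 3.3.1, state that the permanent stops in 3.2 and 4.1 to 4.5 prevail unless an exception is named in the section that sets the stop.
3. In 4.4 and 4.3, name each exception the sponsor means to keep, for example grade 3 fever clearing within 48 hours, or non-hypersensitivity infusion reactions in responders. Without this, step 2 would cancel what step 1 leaves of the exclusion wherever 4.4 applies. 4.3 already does this for skin events.
4. In 4.1, handle any grade 3+ reaction as severe.

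The cost is protocol wording only, with no added visits, procedures, patients or analyses. The downside is that a few patients with possible benefit may stop the drug. Naming intended exceptions limits that, and which ones to keep is a clinical choice for the sponsor.

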4.4 Treatment of \geq Grade III Non-autoimmune-mediated Adverse Events

Treatment for any \geq Grade III adverse event not felt to be due to an autoimmune process may be treated as clinically indicated. No further doses of MDX-010 will be given once a patient experiences a non-skin-related \geq Grade III adverse event attributable to the investigational agents.

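### For a resolved severe non-skin autoimmune event managed without systemic steroids, protocol 3.3.1 can leave MDX-010 dosing open where 4.3 bars it, and neither section is given precedence

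*Protocol*

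**What the plan says.** Protocol 3.3.1 (Treatment Modifications) lists the adverse events, possibly or probably related to MDX-010, for which patients discontinue. Its third bullet covers autoimmune toxicity above grade 2, but only if the event "has the potential to be life threatening with continued antibody administration and is not associated with a potential therapeutic response", and "except rash, vitiligo or asymptomatic autoantibody detection". Other bullets stop treatment when systemic steroids are needed, when an autoimmune toxicity of any grade has not resolved by the time the next dose is considered (a delay of up to 3 weeks is allowed), and for symptomatic uveitis or episcleritis.

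Protocol 4.3 (Supportive Care) says that no further MDX-010 is given after a "Grade III non-skin-related autoimmune adverse event attributable to the investigational agents or if the patient requires systemic steroid therapy", the threshold being Grade III or higher. It contains no life-threatening test, no response exemption and no allowance for resolution. It lists locally delivered steroids and other supportive care among the possible treatments. Its one reference to 3.3.1 concerns skin events.

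On fever, the infusion-reaction bullet of 3.3.1 stops treatment at grade 3 or higher "except for Grade 3 fever that resolves within 48 hours". Section 4.4, for events not thought to be autoimmune, says "No further doses of MDX-010 will be given once a patient experiences a non-skin-related" event of Grade III or higher attributable to the agent, and makes no exception for fever.

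**The concern.** Both sections decide whether a patient with a severe autoimmune event is dosed again, and they use different tests. Section 3.3.1 asks for grade plus two further judgements. Section 4.3 asks only for grade, attribution and a non-skin site. A site working from the treatment-modification section could re-dose a patient whom the supportive-care section excludes.

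Two things are at stake. The first is patient safety, since the decision concerns renewed exposure after a severe toxicity. The second is how the safety report is read. SAP 5.6 summarizes total dose and number of doses by group, and SAP 5.4 summarizes reasons for discontinuation. If the same event ends treatment for one patient and not for another, both summaries mix the effect of the toxicity with the choice of section.

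**Working it through.** The plan gives no figure to reproduce here. The main check applies both sections to the same event.

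**Test event:** Grade 3 or higher, non-skin, non-ocular, autoimmune, judged possibly or probably related to MDX-010.

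| Case | 3.3.1 | 4.3 | Agree? |
|---|---|---|---|
| (a) Resolved, no systemic steroids, judged not potentially life threatening | No stop criterion met | No further dose | No |
| (b) Resolved, no systemic steroids, judged linked to a possible response | Third bullet not met | No further dose | No |
| (c) Potentially life threatening and not response-linked | Stop | No further dose | Yes |
| (d) Systemic steroids needed | Stop | No further dose | Yes |
| (e) Unresolved when the next dose is considered | Stop | No further dose | Yes |

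The difference is confined to (a) and (b). Case (a) concerns mainly grade 3, because the general grade table in 7.4 defines grade 4 as life threatening or disabling. Ocular events have their own rules in 3.3.1 and 4.5 and are left out. Cases (a) and (b) are foreseeable because 4.3 itself provides for treatment other than systemic steroids.

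**Does another part settle it?** Note 7 to the protocol schedule, and note 7 to SAP Table 2, require toxicities of grade 1 or less after the first course before a second one. That governs later courses, not doses within a course. Nothing else in either document ranks 3.3.1 against 4.3.

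**Can 4.3 simply override?** If 4.3 always governs, every attributable non-skin event above grade 2 stops treatment, and the third bullet's two conditions have no effect for non-skin events. They would still work only for skin events other than rash and vitiligo.

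**Fever.** A grade 3 infusion fever attributable to MDX-010, not autoimmune, that resolves within 48 hours is exempt from stopping under 3.3.1. Under 4.4 it is a non-skin event of the barred grade. The form of the mismatch is the same.

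**Size.** No event rate is given, so assume that a proportion p of patients have any attributable Grade 3 or higher non-skin autoimmune event, with p from 5% to 20%. Each group's first stage has 21 patients (protocol 5.5).

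- Expected number: 21 × 0.05 = 1.05 to 21 × 0.20 = 4.2.
- P(at least one) = 1 − (1 − p)^21. At 5%: 1 − 0.95^21 = 0.66. At 20%: 1 − 0.80^21 = 0.99.

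These count cases (a) to (e) together, so they are upper bounds for (a) and (b). To illustrate, suppose a share of 25% to 50% of such events fall in (a) or (b), which is again an assumption:

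- p = 5%: rates 0.0125 and 0.025; 1 − 0.9875^21 = 0.23 and 1 − 0.975^21 = 0.41.
- p = 20%: rates 0.05 and 0.10; 1 − 0.95^21 = 0.66 and 1 − 0.90^21 = 0.89.

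**The case against.** The strongest reply is that 3.3.1 lists reasons to stop and never orders a further dose, so a site can comply with both sections by stopping whenever either one says so. This stands in part: the opposition is between not stopped and barred, not between two contrary instructions. It does not remove the problem. Neither document tells sites to read the sections together, and that reading empties the third bullet's conditions for non-skin events.

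It is also fair to say that the data would not be lost. SAP section 5 lists all data individually, Listings 3.1 and 7.1 cover dosing and adverse events, and the adverse event form codes permanent discontinuation. Dosing after a severe event can therefore be reconstructed, and an extra table row is a convenience.

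Two stronger readings are tempting and are not supported:

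- **The conflict bears on the responder count.** A reader might infer this because the protocol says that experience with MDX-010 "has shown a correlation between severe autoimmunity and tumor response". That experience is in melanoma and renal cell cancer, and stopping the drug does not by itself remove a response from the count. SAP 5.10 reports no clinical response in the first stage and SAP 5.8 drops the efficacy analysis, so no boundary decision is shown to have turned on it.
- **The conflict decides which events count toward the accrual hold.** A reader might infer this because the hold in 3.3.1 applies to toxicities "except for those noted above, that cannot be alleviated or controlled by appropriate care". The hold counts only toxicity still uncontrolled 14 days after care begins, so most resolved events would not reach it. What its exemption covers is a separate question that does not depend on the dosing bar in 4.3.

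**Conclusion.** The inconsistency is real and narrow. It applies to attributable Grade 3 or higher autoimmune events that are non-skin and non-ocular, are managed without systemic steroids, resolve before the next dose, and are judged not potentially life threatening or associated with a possible response. Elsewhere the two sections reach the same result. The fever mismatch between 3.3.1 and 4.4 is a smaller instance.

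This conclusion rests on the wording alone and needs no event rate. Its frequency cannot be fixed from the documents. The 66% to 99% chance of at least one case per 21 patients depends on the assumed 5% to 20% rate and is a ceiling; the share of events falling where the rules differ is unknown. The point should be corrected because it governs re-dosing after severe toxicity and the correction is cheap. The documents do not show that any patient was handled inconsistently, or that an efficacy decision was affected.

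**What to change.** Reconcile the third bullet of 3.3.1 with 4.3, and the fever exemption in 3.3.1 with 4.4. Either state one rule identically in both places or say which section takes precedence. Which rule applies is for the sponsor and investigator to decide; this review takes no position on it.

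Optionally, add to the SAP safety tables a count by group of patients who received MDX-010 after an attributable Grade 3 or higher non-skin autoimmune event. The planned listings already hold the data.

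The cost is a protocol wording amendment and, if the option is taken, one table row. No extra patients, visits or procedures are needed.
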